11.5.2 Clinical Laboratory Assessments

Parts A

Blood and urine samples will be analyzed at a central laboratory with the exception of urine pregnancy tests, which will be analyzed locally. All blood samples will be collected while subjects are in a seated or supine position. Specific instructions for the collection, processing, and shipment of samples will be provided in a separate Laboratory Manual. Laboratory test results that are abnormal and considered clinically significant must be reported as AEs (see Section 13.1.1.2).

Blood and urine samples for clinical laboratory assessments will be collected according to the schedule of assessments (Table 3-1).

Table 11-2 Safety Laboratory Test Panels

Serum Chemistry	Hematology	Urinalysis ^a
Glucose	Hemoglobin	Leukocyte esterase
Blood urea nitrogen ^b	Erythrocytes	Nitrite
Creatinine	Mean corpuscular volume	Urobilinogen
Sodium	Platelets	Urine protein
Potassium	Reticulocytes	pH
Calcium	Leukocytes	Urine blood
Chloride	Differential (absolute and percent):	Specific gravity
Magnesium	Eosinophils	Urine ketones
Bicarbonate	Basophils	Urine bilirubin
Inorganic phosphate	Neutrophils	Urine glucose
Total and direct bilirubin	Lymphocytes	
Alkaline phosphatase	Monocytes	
Aspartate transaminase	Coagulation Studies	
Alanine transaminase	Activated partial thromboplastin time	
Amylase	Prothrombin time	
Lipase	Prothrombin time International	
Gamma-glutamyl transferase	Normalized Ratio	
Protein		
Albumin		
Creatine kinase		
Total cholesterol		
Lactate dehydrogenase		
Laciate denydrogenase		

Note: Haptoglobin may be analyzed if judged to be clinically appropriate by the investigator.

Clinical laboratory assessments from screening will have no clinically significant findings that preclude participation in the study, as deemed by the investigator, for a subject to receive study drug on Day 1.

Liver function testing (ALT, AST, GGT, ALP, and total bilirubin) must be performed at the scheduled visits and Week 20 (a minimum of every 4 weeks after Week 4). A local laboratory may be used for the Week 20 sample if a subject cannot return to the site for the blood draw; confirmatory testing by the central lab must be performed as soon as possible if liver function tests are determined to be abnormal.

Pregnancy (β-human chorionic gonadotropin) Tests for Females of Childbearing Potential: Any female subject who does not meet the criteria for non-childbearing potential is considered to be of childbearing potential and must have a serum pregnancy test at screening. A definition of non-childbearing potential is provided in Section 11.5.6.1. Serum pregnancy tests will be performed at the study site and analyzed at the central laboratory. Urine pregnancy tests will either be performed and analyzed at the site or, when there is no clinic visit scheduled, at home by using a home kit provided by the site. Results will be reported to the site by telephone. The urine pregnancy test on Day 1 must be negative before the first dose of study drug. Additional pregnancy tests may be required according to local regulations and/or requirements.

^a If urinalysis results are positive for leukocyte esterase, nitrite, protein, or blood, microscopic examination of urine will be performed, and results will be provided for leukocytes, erythrocytes, crystals, bacteria, and casts.

If blood urea nitrogen cannot be collected, urea may be substituted.

CF genotype (Screening Period only): CF genotyping will be performed on all subjects to confirm the genotype documented in the subject's medical record. This assessment does not need to be repeated in the case of rescreening

Drug and Alcohol Screening (Screening Period [Parts A and Day 1 [Part A Only]): opiates, methadone, cannabinoids, cocaine, amphetamines/methamphetamines, barbiturates, benzodiazepines, cotinine, and alcohol will be assessed by a urine test. Subjects may undergo random urine drug screen and alcohol testing if deemed appropriate by the investigator. Drug screen result will be negative for all subjects to receive study drug.

Additional Evaluations: Additional clinical laboratory evaluations will be performed at other times if judged by the investigator to be clinically appropriate.

For the purposes of study conduct and unless noted otherwise, only laboratory tests done in the central laboratory may be used. Local laboratories may be used at the discretion of the local investigator for management of urgent medical issues. If a local laboratory test value is found to be abnormal and clinically significant, it will be verified by the central laboratory as soon as possible after the investigator becomes aware of the abnormal result. If it is not possible to send a timely specimen to the central laboratory (e.g., the subject was hospitalized elsewhere), the investigator may base the assessment of an AE on the local laboratory value.

11.5.3 Physical Examinations and Vital Signs

Parts A

A PE of all body systems and vital signs assessment will be performed at screening and select study visits. At other visits, symptom-directed PEs and symptom-directed vital signs assessments can be performed at the discretion of the investigator or healthcare provider.

A PE includes a review of the following systems: head, neck, and thyroid; eyes, ears, nose, and throat (EENT); respiratory; cardiovascular; lymph nodes; abdomen; skin; musculoskeletal; and neurological. Breast, anorectal, and genital examinations will be performed when medically indicated. After screening, any clinically significant abnormal findings in PEs will be reported as AEs.

Symptom-directed PEs and symptom-directed vital signs assessment may be performed if appropriate.

Weight, height, and BMI (derived) will also be assessed (Section 11.4.4).

Vital signs include blood pressure (systolic and diastolic), temperature, pulse rate, and respiration rate. These will be assessed following at least a 5-minute rest in the seated or supine position.

Arterial oxygen saturation by pulse oximetry will be assessed following at least a 5-minute rest and before study drug dosing. At visits when study drug is taken at the site, pulse oximetry will be collected before study drug dosing.

11.5.4 Electrocardiograms

Parts A

Standard 12-lead ECGs will be performed using a machine with printout. Additional standard 12-lead ECGs will be performed at any other time if clinically indicated. The performance of all ECGs will adhere to the following guidelines:

- The ECG will be done before any other procedures that may affect heart rate, such as blood draws.
- The subject will be instructed to rest for at least 5 minutes before having an ECG.
- ECGs will be performed in triplicate at the Day 1 Visit.

A printout of the ECG traces will be made for safety review by the investigator and maintained with source documentation. Clinically significant ECG abnormalities occurring during the study through completion of study participation will be recorded as AEs.

To ensure safety of the subjects, a qualified individual at the study site will make comparisons to baseline measurements. If the QTcF is increased by >60 msec from the baseline or an absolute QTcF value is ≥500 msec for any scheduled ECG, 2 additional ECGs will be performed approximately 2 to 4 minutes apart to confirm the original measurement. If either of the QTcF values from these repeated ECGs remains above the threshold value (>60 msec from baseline or ≥500 msec), a single ECG will be repeated at least hourly until QTcF values from 2 successive ECGs fall below the threshold value that triggered the repeat measurement. A subject with a QTcF value above the threshold value will discontinue dosing.

11.5.5 Ophthalmologic Examination

Parts A

Ophthalmologic examinations do not need to be completed if there is documentation of bilateral lens removal for the subject.

All examinations will be conducted by a licensed ophthalmologist or optometrist and will include:

- measurement of best-corrected distance visual acuity of each eye; and
- pharmacologically dilated examination of the lens with a slit lamp.

The screening examination does not need to be conducted if there is documentation of an examination meeting the protocol requirements that was conducted within 3 months before the date of informed consent.

Any clinically significant abnormal findings will be reported as AEs.

11.5.6 Contraception and Pregnancy

Parts A

The effects of VX-659 monotherapy or in TC with TEZ and IVA on conception, pregnancy, and lactation in humans are not known. VX-659, TEZ, and IVA did not show genotoxic potential in a standard battery of in vitro (Ames test, chromosomal aberration, or micronucleus in cultured mammalian cells) and in vivo (rodent micronucleus) studies. Reproductive toxicology studies of VX-659, TEZ, and IVA have not shown teratogenicity in rats and rabbits.

11.5.6.1 Contraception

Parts A

Contraception requirement for a couple is waived for the following:

- True abstinence for the subject, when this is in line with the preferred and usual lifestyle of
 the subject. Periodic abstinence (e.g., calendar, ovulation, symptothermal, postovulation
 methods) and withdrawal are not acceptable methods of contraception. True abstinence must
 be practiced from the Screening Visit through 90 days after the last dose of study drug.
- If the male is infertile (e.g., bilateral orchiectomy). If a male subject is assumed to have complete bilateral absence of the vas deferens, infertility must be documented before the first dose of study drug (e.g., examination of a semen specimen or by demonstration of the absence of the vas deferens by ultrasound).
- If the female is of non-childbearing potential. To be considered of non-childbearing potential, the female must meet at least 1 of the following criteria:
 - Postmenopausal: Amenorrheic for at least 12 consecutive months and a serum follicle-stimulating hormone (FSH) level within the laboratory's reference range for postmenopausal females
 - o Documented hysterectomy or bilateral oophorectomy/salpingo-oophorectomy

Note: All other females 10 years of age and older (including females with tubal ligations) will be considered to be of childbearing potential.

Same-sex relationships

For subjects for whom the contraception requirement is not waived, study participation requires a commitment from the subject that at least 1 acceptable method of contraception is used as a couple. Methods of contraception must be in successful use from signing of consent (or assent, when applicable), approximately 28 days before the first dose of study drug (unless otherwise noted), and until 90 days following the last dose of study drug. Additional contraception requirements may need to be followed according to local regulations and/or requirements. Acceptable methods of contraception are listed in Table 11-3.

Table 11-3 Acceptable Methods of Contraception

	Male Subjects and Their Female (Non-study) Partners	Female Subjects and Their Male (Non-study) Partners
Vasectomy performed at least 6 months previously, with a documented negative postvasectomy semen analysis for sperm	Yes	Yes
Bilateral tubal occlusion (e.g., ligation) performed at least 6 months previously	Yes	Yes
Male or female condom with or without spermicide ^a	Yes	Yes
Female barrier contraception (such as diaphragm, cervical cap, or sponge) with spermicide	Yes	Yes
Continuous use of an intrauterine device for at least 90 days before the first dose of study drug		
Hormone-releasing	Yes	No ^b
Non-hormone releasing	Yes	Yes
Hormonal contraceptives, if successfully used for at least 60 days before the first dose of study drug	Yes	No ^b

^a A female condom cannot be used with a male condom due to risk of tearing.

Additional notes:

- If over the course of the study the subject meets the criteria for waiving the contraception requirements, the subject does not need to follow the contraceptive methods listed in Table 11-3.
- Male subjects must not donate sperm during the period starting from the first dose of study drug until 90 days after the last dose of study drug.
- Female subjects should not nurse a child during the period starting from the first dose of study drug until 90 days after the last dose of study drug.
- For male subjects with a female partner of childbearing potential, the couple should not plan to become pregnant during the study or within 90 days after the last dose of study drug, with the exception of couples who plan to become pregnant by artificial insemination using sperm banked by the male subject before the first dose of study drug or sperm from another source.

11.5.6.2 Pregnancy

Parts A

Subjects will be counseled to inform the investigator of any pregnancy that occurs during study treatment and for 90 days after the last dose of study drug.

If a female subject becomes pregnant during study participation, study drug will be permanently discontinued immediately. The investigator will notify the medical monitor and Vertex Global Patient Safety (GPS) within 24 hours of the site's knowledge of the subject's (or partner's) pregnancy using the Pregnancy Information Collection Form. Male subjects with female partners

Hormone-releasing intrauterine devices and hormonal contraceptives are not considered an acceptable method in female study subjects due to potential induction of metabolism by VX-659; however, female subjects are not required to discontinue their use of hormone-releasing intrauterine devices or hormonal contraceptives.

who become pregnant during the study must use a male condom to avoid exposure of a potential embryo or fetus to study drug via the seminal fluid.

If confirmed to be on active drug, the subject or partner will be followed until the end of the pregnancy and the infant will be followed for 1 year after the birth, provided informed consent is obtained. A separate ICF will be provided to explain these follow-up activities. Pregnancy itself does not constitute an AE.

12 STATISTICAL AND ANALYTICAL PLANS

[figure not shown]
Parts A

This section presents a summary of the planned analyses for this protocol. Statistical analysis details will be provided in the statistical analysis plan (SAP), and clinical pharmacologic analysis details will be provided in the clinical pharmacology analysis plan (CPAP), both of which will be finalized before the clinical data lock for the study.

12.1 Sample Size and Power

Part A

Approximately 12 subjects will be enrolled in Part A. Sample size calculations were determined based on VX-659 PK, using noncompartmental analysis (NCA)-based parameters, such as clearance and volume of distribution. Based on the variability observed in adults, data from 12 subjects will allow 80% power to target a 95% CI within 60% and 140% of the geometric mean estimate of clearance for VX-659.

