A schematic of the study design for Part A is provided below. Approximately 12 subjects (F/F or F/MF genotypes) are planned for enrollment. During the Treatment Period, subjects will be administered VX-659/TEZ/IVA for approximately 15 days. A review of safety, tolerability, and available PK data will be completed by an internal Vertex team after Part A

Additional subjects may be enrolled as needed in Part A,

based on emerging PK data,

[figure not shown]
Part A Study Design

IVA: ivacaftor; n: number of subjects; TEZ: tezacaftor

VX-659/TEZ/IVA will be administered from Day 1 through Day 15. On Day 15, only the morning dose will be administered.

Parts A Doses			
Subjects Weight	VX-659 Dose	TEZ Dose	IVA Dose
Part A			
All weights	$120 \mathrm{mg} \mathrm{qd}$	50 mg qd	75 mg q12h

IVA: ivacaftor; qd: daily; q12h: every 12 hours; TEZ: tezacaftor

[figure not shown]
Assessments Parts A

PK Assessments:

- PK parameters for VX-659, TEZ, and IVA
- PK parameters for TEZ and IVA metabolites

Safety Assessments:

AEs, clinical laboratory assessments (serum chemistry, hematology, coagulation studies, and urinalysis), standard 12-lead ECGs, vital signs, pulse oximetry, ophthalmologic examinations, and physical examinations (PEs)

Statistical Analyses

Data from Parts A will be analyzed separately.

Part A

Approximately 12 subjects will be enrolled in Part A. Sample size calculations were determined based on VX-659 PK using noncompartmental analysis-based parameters, such as clearance and volume of distribution. Based on the variability observed in adults, data from 12 subjects will allow 80% power to target a 95% CI within 60% and 140% of the geometric mean estimate of clearance for VX-659.

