8.1 Inclusion Criteria

Parts A

Subjects who meet all of the following inclusion criteria will be eligible for Part A

- 1. Subject (or his or her legally appointed and authorized representative) will sign and date an informed consent form (ICF), and an assent form.
- 2. Subjects (males and/or females), 6 through 11 years of age, inclusive, on the date of informed consent.
- 3. Subjects who weigh ≥15 kg without shoes at the Screening Visit.

- 4. Confirmed diagnosis of CF as determined by the investigator.
- Subjects who are homozygous for F508del (F/F genotype) or heterozygous for F508del and a
 minimal function mutation that is not responsive to TEZ, IVA, or TEZ/IVA (F/MF
 genotypes; Appendix A).
 - Genotype should be confirmed at the Screening Visit.
 - If the screening *CFTR* genotype result is not received before the first dose of study drug, a previous *CFTR* genotype laboratory report may be used to establish eligibility.
 - Subjects who have been enrolled and whose screening genotype does not confirm study
 eligibility must be discontinued from the study (Section 9.9).
- Subjects with FEV₁ ≥40% of predicted normal for age, sex, and height using equations of the Global Lung Function Initiative (GLI)⁶ at the Screening Visit (Section 11.4.1).
- 7. Subjects with stable CF disease as deemed by the investigator at the Screening Visit.
- 8. Subjects who are willing to remain on a stable CF medication regimen (other than CFTR modulators) through Day 15 (**Part A**) or, if applicable, through the Safety Follow-up Visit.
- 9. Subjects who are able to swallow tablets.
- Female subjects of childbearing potential must have a negative serum pregnancy test at the Screening Visit.
- 11. Subjects of childbearing potential and who are sexually active must meet the contraception requirements outlined in Section 11.5.6.1.
- 12. As deemed by the investigator, the subject's legally appointed and authorized representative (e.g., parent or legal guardian) AND the subject must be able to understand protocol requirements, restrictions, and instructions. The subject's legally appointed and authorized representative should be able to ensure that the subject will comply with and is likely to complete the study as planned.

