9.3.3 Study Drug Dose and Duration

Parts A

VX-659 Dosage

A VX-659 dose of 240 mg once daily (qd) is currently under evaluation in ongoing Phase 3 studies of adult and adolescent (\geq 12 years of age) CF subjects with an F/MF or F/F genotype. The 240 mg dose was selected based on an assessment of the benefit-risk profile from Phase 2 Study VX16-659-101 (Study 659-101), which evaluated a range of VX-659 doses (80 mg qd, 240 mg qd, and 400 mg qd) in TC with TEZ/IVA in subjects with F/MF and F/F genotypes. In Study 659-101, the TC was generally safe and well tolerated in all VX-659 dose groups. Subjects with F/MF genotypes who received the VX-659 240 mg qd TC demonstrated a clinically meaningful improvement in ppFEV₁ (within-group mean [SE] absolute change of 11.6 [2.1] percentage points from baseline [P<0.0001], compared with a mean absolute change of 0.3 [2.8] percentage points in subjects who received placebo [P = 0.9053]). The improvement

in ppFEV₁ for VX-659 400 mg qd in TC with TEZ/IVA was similar to improvements for VX-659 240 mg qd.

The VX-659 dose of 120 mg qd selected for evaluation in the current study was determined based on population-PK modeling utilizing data from adults and simulating exposure over a range of body weights typical for a population of 6 to <12 year-olds, ranging from 15 to 50 kg. The simulations indicate that a dose of 120 mg qd is predicted to provide similar exposures to that observed in adults dosed with 240 mg qd, up to a body weight of approximately 40 kg. At a body weight of 40 kg or higher, exposure of VX-659 following dose of 120 mg is predicted to be low relative to that of adults dosed with 240 mg qd. At ≥40 kg, a dose of 240 mg qd is predicted to provide similar exposure to that of adults. A single dose level of 120 mg qd will be evaluated in Part A to confirm the appropriateness of the doses

Therefore, the dose selected for evaluation in Part A is predicted to be safe.

TEZ and IVA Dosages

TEZ will be administered as 50 mg qd and IVA will be administered as 75 mg every 12 hours (q12h) in all subjects in Part A

Part A

Duration of Dosing

The 15-day duration of dosing was chosen to provide an adequate assessment PK, safety, and tolerability of VX-659/TEZ/IVA

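### Does resting n = 12 on adult clearance variability, with no CV given and no word on body weight, undermine the 80% power stated in Section 12.1?

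*Protocol*

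**What the plan says.** Section 12.1 sets the size of Part A: "Approximately 12 subjects will be enrolled in Part A". The calculation uses noncompartmental parameters such as clearance and volume of distribution. The precision claim is "Based on the variability observed in adults, data from 12 subjects will allow 80% power to target a 95% CI within 60% and 140", the limits being percentages of the estimated geometric mean of VX-659 clearance. The synopsis repeats this. Neither place gives the adult CV or says whether clearance is absolute or weight-adjusted.

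Section 9.3.3 reports population-PK simulations over 15 to 50 kg. The lower dose, 120 mg once daily, comes out as "predicted to provide similar exposures to that observed in adults dosed with 240 mg qd, up to a body weight of approximately 40 kg". From 40 kg, 120 mg is predicted to give low exposure relative to those adults, and "At ≥40 kg, a dose of 240 mg qd is predicted to provide similar exposure to that of adults". Part A gives 120 mg qd at every weight. Section 8.1 sets a floor, "Subjects who weigh ≥15 kg without shoes at the Screening Visit", and no ceiling.

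Section 12.4.1 allows nonlinear mixed-effects modelling and/or noncompartmental analysis, summarises PK parameters descriptively, and leaves the detail to the clinical pharmacology analysis plan. The synopsis adds: "Additional subjects may be enrolled as needed in Part A".

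**The concern.** PK is the primary objective of Part A, and the sentence in Section 12.1 is the only visible basis for 12 subjects. Without the CV, a reader cannot recompute the 80%.

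Section 9.3.3 sharpens the worry. Clearance is dose divided by AUC. If 120 mg below about 40 kg and 240 mg from 40 kg up both reproduce the adult AUC on 240 mg, clearance is about 120/240 = 0.5 of the adult value in the lighter children and about 1.0 in the heavier ones. A sample from both groups would then show more spread in unadjusted clearance than adults do. If the adult CV was used as it stood, the interval could be wider than planned and the true power below 80%.

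**Working it through.** **Inputs.** From Section 12.1: n = 12, 95% confidence, 80% power, limits 60% and 140% of the geometric mean. From Section 9.3.3: doses of 120 and 240 mg, and a weight boundary near 40 kg. Assumed, because the protocol does not give them: the adult CV, the clearance ratio R between weight groups, and the number k of 12 children at 40 kg or more.

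**Step 1: the plan's own figure.** A geometric mean points to the log scale. The upper limit binds, since ln 1.4 = 0.336 is smaller than −ln 0.6 = 0.511. Then

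power = P( t(0.975, n−1) · S/√n ≤ ln 1.4 ), with (n−1)S²/σ² distributed as chi-square on n−1 df.

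For n = 12, t = 2.201, so S must not exceed 0.3365 × 3.464 / 2.201 = 0.5296. The 80th percentile of chi-square on 11 df is 14.63, so the largest σ giving 80% is 0.5296 × √(11/14.63) = 0.459. With CV = √(exp(σ²) − 1), that is a CV of 48.4%. The 80% cannot be reproduced without the CV, but it holds for any total CV up to 48.4%. At CVs of 40%, 50% and 60% the power is 96%, 76% and 47%. On an arithmetic scale (mean ± 40%) the limit would be 54.6%.

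**Step 2: an added weight effect, clearance unadjusted.** Let k of 12 children have clearance R times that of the rest. Then (n−1)S²/σ² is noncentral chi-square on 11 df with λ = 12·p(1−p)·(ln R)²/σ², p = k/12, where σ is the log-SD within each weight group.

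| R | k | Largest within-group CV keeping 80% | Power at CV 30% | CV 40% | CV 50% |
|---|---|---|---|---|---|
| 1.5 | 1 | 46.7% | >99% | 94% | 71% |
| 1.5 | 2 | 45.2% | >99% | 92% | 67% |
| 1.5 | 3 | 44.1% | >99% | 89% | 64% |
| 2 | 1 | 43.2% | 99% | 88% | 61% |
| 2 | 2 | 38.8% | 96% | 77% | 50% |
| 2 | 3 | 35.3% | 91% | 68% | 42% |

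With k = 0 or R = 1, nothing is lost.

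**Step 3: how many more subjects.** If the adult CV sits exactly at 48.4%, restoring 80% takes 14, 15 or 16 subjects for R = 2 with k/12 = 1/12, 2/12 or 3/12, and 13 or 14 for R = 1.5.

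**Step 4: is it a step at 40 kg?** The ratio of 2 comes from reading similar exposure as equal exposure in both groups. The dose needed to match adults is described in two bands; predicted clearance may rise smoothly. As an illustration, let clearance scale with weight to the power 0.75 (an assumption), with weights uniform over 15–50 kg. The geometric mean ratio of the heavier to the lighter group is then about 1.5, and children of 41 and 39 kg differ by (41/39)^0.75 − 1, about 4%. Such a gradient still costs power if clearance is unadjusted: power is 97%, 80% and 58% at residual CVs of 30%, 40% and 48%.

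**The case for a change.** The best case for a change is that n is already fixed by a calculation in Section 12.1, so a plan finalised before data lock cannot supply its basis afterwards. The protocol's own predictions also imply that clearance varies with weight in the eligible range, and that holds for a smooth gradient as well as for a step. If the adult CV is in the 40s and clearance is unadjusted, the real power could be well below 80%: 54% at a CV of 48.4% with R = 2 and k = 2. Stating the CV and the clearance scale would cost a sentence or two.

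Part of this stands. The CV and the handling of weight are missing, and stating them would be good practice.

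The rest does not show that the plan goes wrong. The loss needs several unknowns to line up: an adult CV near the limit, unadjusted clearance, a ratio near 2 and several children at 40 kg or more. At a CV of 35%, even R = 2 with k = 3 keeps 81%. The adult figure may also already contain some spread due to adult weight. Section 12.1 says nothing about weight that Section 9.3.3 contradicts, and Section 9.3.3 shows that the sponsor already models exposure by weight. The lack of a CV benchmark for adding subjects cannot be held against the plan, because the sentences on additional enrolment are cut off in the public text.

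**Conclusion.** No change to the plan is needed. Section 12.1 leaves out the adult CV and whether clearance is weight-adjusted, but no stated number or rule is shown to be wrong. The 80% holds on the log scale for any total CV up to about 48%. If clearance is unadjusted and weight adds spread, the tolerable adult CV is about 35–47%, assuming a 1.5- to 2-fold difference and 1 to 3 of 12 children at 40 kg or more. The protocol supports a weight-related difference of uncertain size, not a proven twofold step.

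The consequence is also limited. Part A has no pass/fail test on this interval; PK is summarised descriptively. The interval will be computed from the children's own data, so a larger spread would show as a wider interval and would not be hidden. Section 12.4.1 permits population modelling, where weight can enter as a covariate, and leaves the method to the clinical pharmacology analysis plan. Even the worst case in Step 3 asks for 16 subjects, and the protocol lets Part A enrol more. Analysts following the plan would still reach sound results, so this is an unstated input that they can fill sensibly.
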